8.2 Efficacy Endpoints

8.2.1 Food Challenge Symptom Score

Total number of symptoms for a given individual and proportion of a specific symptom among all subjects. Clear objective or persistent subjective symptoms are typically reasons to stop and treat a patient.

8.2.2 Change in Immune Parameters

There are numerous parameters: peanut specific IgE, peanut specific IgG4, skin test size, basophil reactivity, TH2 cytokine release, and T regulatory levels. These were drawn annually and at the final challenge(s).

9. STUDY PATIENTS AND DEMOGRAPHICS

9.1 Disposition of Patients and Withdrawals

The numbers and percentage of patients enrolled, completing the 48th month and final DBPCFCs, and withdrawing from the study, along with reasons for withdrawal, will be tabulated. In addition, the number of patients discontinuing during the SU phase will be summarized. The number and percentage of patients in each analysis population will be reported. This summary will be based on all patients who have data entered into the database.

9.2 Protocol Violations and Deviations

Protocol violations and deviations will be checked on complete data for all patients. The final decision regarding inclusion and exclusion of patients from the analysis populations will be based on a listing of protocol violations and deviations. This will be determined during a (blinded) data review meeting before database lock and the final analysis with input from Clinical and statistical teams.

Protocol violations and deviations will be summarized by type for the Safety population. Individual patients with protocol deviations or violations will be listed.

9.3 Demographics and Other Baseline Characteristics

Descriptive summaries of the demographic and other baseline characteristics will be completed for all enrolled patients in the study population, unless otherwise specified.

Descriptive summaries of demographic and other baseline conditions will include:

- Demographics
 - Age at onset of study (1-11 yrs)
 - Sex (M/F)
 - Age at introduction of peanut (0-11 yrs)
 - Daycare (Y/N)
- History
 - Concurrent eczema (Y/N)
 - Concurrent asthma (Y/N)
 - Concurrent allergic rhinitis (Y/N)
 - Parental history of atopic disease (Non/Mother/Father/Both)
 - C-section (Y/N)
 - Breastfeeding (Y/N)
 - Milk allergy (Y/N)
 - Egg allergy (Y/N)
- Clinical
 - Initial peanut skin test size (3mm-30mm)
 - Initial peanut IgE level (0.35-100kU/L)

Medical History will be coded using the latest version of MedDRA (version 16.0) and summarized by SOC and Preferred Term using frequency counts. Physical exam data will be presented in listings.

10. EFFICACY ANALYSES

10.1 Primary Efficacy Analysis Approach

To begin with, our primary analysis will comprise of two parts.

First, an Interval-Censoring Survival Analysis (ICSA) approach will be used to analyze the 48th month DBPCFC threshold data (Collett, 1993, Chapter 9, Taylor et al - 2009). The methodology is appropriate when the exact dose that provokes a reaction in an individual is not known but it is known to fall into a particular interval. Using ICSA, if an individual had an objective reaction at the first dose in a challenge trial, then left-censoring occurred, and the NOAEL was set to zero with the LOAEL set as that first dose. If an individual did not experience an objective reaction after the largest challenge dose, then right-censoring occurred, and the NOAEL was set to that largest challenge dose (if a subjective response occurred at that largest dose, this was also considered as the objective NOAEL), while the LOAEL was set to infinity. In all other cases, interval-censoring occurs bounded by the NOAEL and LOAEL. Parametric (Log-normal, Weibull) and non-parametric dose-distribution model will be used to estimate the ED10 and the ED05, the doses predicted to provoke reactions in 10% and 5%, respectively, of the peanut-allergic population.

Second, for each dose interval bounded by the NOAEL and LOAEL of the 48th month DBPCFC, we will conduct survival analysis with case-1 censoring (Huang – Wellner lecture notes, Kosorok et al, 1998) to estimate time to loss of desensitization. We will assume exponential

distribution with log link for the decay of sensitivity threshold for those who take the final challenge. This assumption of exponential decay will be validated using semi/non-parametric analysis with an option for modeling with a more flexible **semi-parametric** distribution. The analyses will be performed with and without the effect of baseline and other clinical covariates. This analysis will provide an initial insight into effectiveness of peanut SLIT in longevity of induced clinical desensitization and SU.

To illustrate, we introduce the following notation. Let X_d be the time to loss of desensitization with distribution F_d for a given NOAEL, d , administered at the 48th month DBPCFC ($d = 100, 200, 500, 800, 1300, 2100$ mg). Let T be an observation time (in weeks), $t = 0, 1 \dots 17$ with distribution G . Because the assignment time is randomized, the time of interest X_d and baseline covariates will be independent of T . We also assume that the clinically induced desensitization is monotonically decreasing such that the subject's NOAEL is either decreased or stays constant by observation time T . In other words, the true time to loss of desensitization from the 48th month DBPCFC, which is unknown, is either less or equal to the observation time. This could mathematically be represented as a problem of case-1 interval censoring wherein, we observe n i.i.d observations of $(T, I\{X_d \leq T\} | d) = (T, \Delta_d)$ for a given NOAEL, d . Further, we assume $X_d = 0$ for those subjects who do not meet MCRT ($d < MCRT$) at the 48th month DBPCFC. Let π define the probability that $X_d = 0$, and let the baseline and clinical covariates be represented by Z . Then, in order to derive the likelihood of F_d , we need to solve the following optimization problem to find the MLE:

$$\sup_{F \in \mathcal{F}} L_n(F)$$

, where \mathcal{F} is a class of distribution functions and

$$L_n(F) = \prod_{i=1..n} P(\beta, \gamma, Z_i, t)$$

$$\begin{aligned} P(\beta, \gamma, Z_i, t) &= \{P(X_{id} = 0) I(X_{id} = 0)\} * \{P(X_{id} > 0) I(X_{id} > 0)\} \\ &* \{P(X_{id} = t, \Delta = 0 | d, X_{id} > 0)\} * \{P(X_{id} = t, \Delta = 1 | d, X_{id} > 0)\} \\ &= \left[\frac{e^{\gamma' Z_i}}{1 + e^{\gamma' Z_i}} \right]^{y_i} * \left[\frac{1}{1 + e^{\gamma' Z_i}} \right]^{1-y_i} * [(1 - F_d(t))g(t)]^{1-\delta_i} * [F_d(t)g(t)]^{\delta_i} \\ &= \left[\frac{e^{\gamma' Z_i}}{1 + e^{\gamma' Z_i}} \right]^{y_i} * \left[\frac{1}{1 + e^{\gamma' Z_i}} \right]^{1-y_i} * (1 - F_d(t))^{1-\delta_i} * F_d(t)^{\delta_i} g(t) \end{aligned}$$

$$y_i = I(X_{id} = 0); \delta_i = I(\Delta_i = 1); F_d(t) = 1 - e^{-\lambda_i t}; \lambda_i(t, Z_i) = \lambda_0 e^{\beta' Z_i}$$

Maximizing the above likelihood will provide estimates of β & γ towards estimating distribution of time to loss of desensitization.

The results from preliminary analyses will help support implementation of advanced and more precise methods to study decrease in threshold using Double Censoring Survival Analysis (DCSA) (Sun et al, 2004) in a stochastic framework to account for changes with time. This will allow estimation of the distribution of decrease in desensitization as a function of time giving an opportunity to estimate population half-life and association between the hazard of loss of desensitization and baseline and clinical covariates.

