#### ***Purpose and expectations:***

This two-part primary objective is designed to estimate the level of desensitization induced by peanut SLIT through determination of the population sensitization threshold and to characterize its potential for SU by calculation of a desensitization decay curve. We expect to demonstrate successful desensitization above the MCRT (300 mg peanut protein) for the population and to demonstrate SU for a period of time between 1 and 17 weeks after discontinuation of peanut SLIT therapy.

The studies under the Primary Objective will determine the level of protection against accidental ingestions of peanut provided by peanut SLIT therapy. These results will further determine whether peanut SLIT can be considered a viable option alongside OIT and EPIT for peanut allergy. In addition, the studies will provide data regarding the duration of the desensitization effect which may have important clinical ramifications on the optimal dosing interval and the effect of missed doses/non-compliance. These results could also shed further insight into the immune mechanisms involved in the development and loss of desensitization.

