3.2 Study Endpoints

3.2.1 Efficacy Endpoints

The primary efficacy endpoints are:

- An estimate of the dose as assessed by the 48th month DBPCFC, also called population sensitization threshold, predicted to provoke reactions in 5% and 10% of the peanut-allergic population. This will also give population level NOAEL and LOAEL that would define interval of consecutive administered dose levels within which the population sensitization threshold lies.
- Multiplicative or differential change in the population sensitization threshold as assessed by the 48th month DBPCFC with a unit change in covariates.
- An estimate of time to loss of desensitization for the following events:
 - Subject's true sensitivity threshold to reduce by half, also called half-life of sensitivity threshold.
 - Subject's true sensitivity threshold to maintain at the same level of LOAEL.
 - Subject's true sensitivity threshold to drop by at least one level of LOAEL.
 - Subject's true sensitivity threshold to remain at or above MCRT.
- Estimates of the proportion of patients at a fixed time for any of the above events that define loss of desensitization (bullet 2).
- Multiplicative change in hazard of loss of desensitization with a unit change in covariates.

Secondary efficacy endpoints include:

- Comparative estimates of changes in immune parameters over time among subjects who were induced with clinical desensitization versus those who failed.

- Incidence of all serious adverse events (SAEs) during the study.

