3.2.3 Endpoint Definitions

- The loss of desensitization is defined as the decline in sensitivity threshold at the final DBPCFC from the 48th month DBPCFC.
- NOAEL is the highest dose observed not to produce any adverse effect and LOAEL is the lowest dose that is observed to produce an adverse effect. Experimentally determined individual's true sensitivity threshold lie between NOAEL and LOAEL. The establishment of individual NOAELs and LOAELs is dependent upon the selection of and spacing between doses selected in the clinical challenge trial design.

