4. OVERALL STUDY DESIGN AND PLAN

This is a Phase 2, open label 52-month study designed to evaluate the safety and efficacy of peanut SLIT in inducing clinical desensitization among peanut allergic children.

The study consists of a Screening visit, a Baseline Visit (sometimes combined with the Screening Visit), a build-up phase (approximately, 20 weeks), a Maintenance phase (42 months) and finally, a Sustained Unresponsiveness phase (17 weeks). The total duration of the study, including Screening and the follow-up period, is approximately 225 weeks. We note that all the 24 subjects that have passed the 48 month time point and have been waiting to be administered the 48th month DBPCFC are continuing to dose daily. Because, based on prior evidence, the benefit of continued dosing past 48 months is considered to be negligible on the overall treatment outcome, a slight extension of maintenance phase is considered negligible for such subject.

Following the qualifying entry 1000 mg peanut protein DBPCFC administered at the baseline, subjects will be administered diluted pumps of concentrated peanut protein extract (5000 mcg/ml) based on the build-up dosing scheme to reach an escalated dose of 4000 mcg. Visits for build-up doses will occur prior to changing peanut dilutions or every 4 weeks. Subjects completing the Duke IRB Pro0003579, UNC IRB 11-2301, CoFAR4 who do not pass the 164 week 10 gm DBPCFC may enroll in this study and resume an escalation schedule starting with the 2000 mcg dose in this SLIT (11-2308, TLC) protocol. This defines the build-up phase.

After completing the escalation schedule, subjects will continue to be administered 4000 mcg of peanut SLIT daily at home and will return to the clinical research unit for follow-up visits every 6 months or more frequently for new or significant symptoms. This defines the maintenance phase.

At the 48th month visit, all subjects undergo a 5000 mg peanut protein DBPCFC to verify desensitization, defined as a reaction threshold greater than MCRT (300 mg of peanut protein). At the same visit, subjects are randomized to one of the 17 weeks of SU phase for administration

of the final DBPCFC to assess SU. SU is claimed if the final DBPCFC reaction threshold is greater than or equal to the larger of MCRT and the 48th month DBPCFC sensitivity threshold. Subjects who fail the 48th month DBPCFC, hence not desensitized, will not be administered the final challenge.

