4.2 Double Blind Placebo Controlled Food Challenge (DBPCFC)

Protocol DBPCFCs will be administered on the subject at entry, 48 months and weekly during the seventeen-week tolerance phase by a nurse or physician who is blinded to the testing material. The supervising investigator will also be blinded to testing material. Before each challenge, the subject will have a physical exam and peak expiratory flow measurements performed.

The DBPCFC consists of two parts that will be randomly ordered. One part will consist of graded doses of peanut flour and the other of identical graded doses of placebo in the form of oat flour. The doses will be given every 10-20 minutes up to a cumulative dose of 1000 mg (25 mg, 50 mg, 100 mg, 250 mg, 575 mg) during the entry challenge and up to a cumulative dose of 5000 mg (100 mg, 200 mg, 500 mg, 800 mg, 1300 mg, 2100 mg) during the 48th month and final DBPCFC. There will be a minimum 10 minute observation period between doses to monitor for symptoms.

After administration of the first part of the challenge the subject will be observed for a minimum period of 1 hour prior to starting the second part. Reactions will be scored using a Food Challenge Symptom Score (FCSS) sheet. If the subject begins to have significant objective or persistent subjective symptoms, the food challenge will be terminated and the subject will be given appropriate treatment. Subjects who are symptomatic and receive treatment are observed for a minimum of 2 hours after the challenges are completed before being discharged from the clinical research unit.

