4.3 Method of Week Assignment for the Final Challenge and Randomization

The following criteria must be satisfied in order for the patient to continue to the SU phase of the study and be randomized:

1. The patient achieves MCRT at the 48th month DBPCFC to continue to the SU phase. This requires patient to be asymptomatic upon administration of 300 mg dose as assessed by Food Challenge Symptom Score sheet.
2. If subjects are found symptomatic and AEs that occur are considered to be intolerable at or below the MCRT, subjects will be refrained from taking the final challenge and will be considered to have lost their desensitization at week 0.
3. No subject will be administered a final challenge dose higher than the NOAEL attained at the 48th month DBPCFC.

Before the start of the SU phase of the study, a computer-generated block randomization schedule is prepared such that each subject has an equal probability of being randomized to one of the weekly challenges held in initial 6 weeks, between 7-12 weeks and between 13-17 weeks. Based on the randomization schedule, three qualified subjects are randomly assigned to one of the final DBPCFC administered each week during the study's 17-week SU phase.

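### The SAP does not name the dose scale behind ED05 and ED10: its listed NOAEL values are single steps, while the 300 mg MCRT exists only as a cumulative dose

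*SAP*

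**What the plan says.** The 48th month and final challenges run "up to a cumulative dose of 5000 mg (100 mg, 200 mg, 500 mg, 800 mg, 1300 mg, 2100 mg" (SAP 4.2; the same steps are in Protocol 5.6).

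On the threshold side, SAP 3.2.3 says that "NOAEL is the highest dose observed not to produce any adverse effect" and gives no scale. SAP 3.2.1 says that the first primary endpoint yields an "interval of consecutive administered dose levels within which the population sensitization threshold lies", and SAP 3.1.1 uses similar wording. SAP 10.1 sets the limits for the ED05/ED10 fit; for a child with no reaction, "right-censoring occurred, and the NOAEL was set to that largest challenge dose". The second part of SAP 10.1 takes the NOAEL and LOAEL of the same challenge and lists the NOAEL as "d = 100, 200, 500, 800, 1300, 2100" mg. It then compares that NOAEL directly with the MCRT.

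On the MCRT side, SAP 4 has desensitization "defined as a reaction threshold greater than MCRT (300 mg of peanut protein"). SAP 4.3 says "This requires patient to be asymptomatic upon administration of 300 mg dose". The Protocol Synopsis and Study Design section word the criterion as an amount the child can consume. Protocol 2.1 gives the expectation: "We expect to demonstrate successful desensitization above the MCRT (300 mg peanut protein) for the population".

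**The concern.** ED05 and ED10 form the first primary endpoint and are reported in milligrams of peanut protein. The protocol says that these results will show how much protection SLIT gives against accidental ingestion, so the meaning of a milligram matters.

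A programmer who follows the only list of NOAEL values in the SAP would enter 2100 mg for a child who tolerated 5000 mg in total. The fit would then return ED05 and ED10 on the step scale, and a reader would set them beside a 300 mg MCRT that belongs to the cumulative scale. If the scale stays open until analysis, it could also be chosen after the data are seen.

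**Working it through.** **1. The plan's own total.** 100 + 200 + 500 + 800 + 1300 + 2100 = 5000 mg, as stated.

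**2. Where 300 mg sits.** No step is 300 mg. The running total after two steps is 100 + 200 = 300 mg. A child whose NOAEL is the 200 mg step has therefore taken 300 mg without a reaction, yet 200 < 300 in the comparison made in SAP 10.1.

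**3. The two scales side by side.** Gap = 1 − step/cumulative.

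| Level | Step (mg) | Cumulative (mg) | Step lower by |
|---|---|---|---|
| 1 | 100 | 100 | 0% |
| 2 | 200 | 300 | 33% |
| 3 | 500 | 800 | 37.5% |
| 4 | 800 | 1600 | 50% |
| 5 | 1300 | 2900 | 55% |
| 6 | 2100 | 5000 | 58% |

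**4. Non-parametric fit.** Recoding changes the interval limits but not the proportion of children in each interval. If ED10 falls in the third interval, it is reported as 200–500 mg on steps and 300–800 mg on cumulative dose. On the cumulative scale 300 mg is an interval limit. On the step scale it lies inside an interval, so the fit cannot say on which side of 300 mg ED10 falls.

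**5. Parametric fit.** The likelihood is the product over children of F(LOAEL) − F(NOAEL). For the log-normal, F(x) = Φ((ln x − μ)/σ) and ED10 = exp(μ − 1.2816σ). The documents give no threshold distribution, so a log-normal on the cumulative scale is an assumption. The same children are coded once with each set of limits. With expected proportions (no sampling error), log-normal ED10 is:

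| Assumed median (mg), log SD | Cumulative ED10 (mg) | Step ED10 (mg) | Step versus cumulative |
|---|---|---|---|
| 300, 1.6 | 39 | 46 | 18% higher |
| 800, 0.8 | 287 | 207 | 28% lower |
| 1600, 1.2 | 344 | 240 | 30% lower |
| 2900, 1.6 | 373 | 257 | 31% lower |
| 4000, 0.8 | 1435 | 744 | 48% lower |

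Hand check of the third row: 1600 × exp(−1.2816 × 1.2) = 344 mg, and 1 − 240/344 = 0.30.

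Over medians of 300–4000 mg, log SD 0.8–1.6, and both log-normal and Weibull fits, the step-scale ED10 runs from 37% above to 49% below the cumulative value. ED05 runs from 76% above to 45% below.

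**6. At the trial's size.** Simulated trials used n = 45 (the number of completers in the Protocol Synopsis), log-normal fits and log SD 1.0 or 1.3:

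| True cumulative ED10 (mg) | Median estimate, cumulative (mg) | Median estimate, step (mg) | Step versus cumulative |
|---|---|---|---|
| 50 | 50–53 | 57–58 | about 10% higher |
| 100 | 102–106 | 88–92 | about 10–15% lower |
| 400 | 404–417 | 261–276 | about 33% lower (median ratio 1.49; 1 − 1/1.49 = 0.33) |
| 500 | 506–524 | 324–332 | about 36% lower (1 − 324/506 = 0.36) |
| 1000 | 1019–1024 | 571 | about 44% lower (1 − 571/1019 = 0.44) |

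**7. Effect on a reading against 300 mg.** As an illustration only, count the trials in which the two codings put the ED10 estimate on opposite sides of 300 mg. This happens in roughly 55–70% of trials at a true ED10 of 400 mg and in about a third at 500 mg. At 50, 100 and 1000 mg it happens in none.

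**The case against.** The strongest reply is that no sentence puts ED05 and ED10 on the step scale. The rule for completers names no scale, and nor does the NOAEL definition. The explicit list belongs to the time-to-loss analysis, where the NOAEL is a conditioning label whose numeric value matters only when it is compared with the MCRT. Both documents call the whole challenge 5000 mg. The cumulative reading of the MCRT is also inferred, and SAP 4.3 words it as a dose. The threshold study cited for the method might settle the scale, but it is not part of these documents.

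This stands in part: the step scale for ED05/ED10 is a strong inference, not a statement. It is strong because SAP 10.1 carries the NOAEL and LOAEL of the same challenge from its first part into its second, lists no other values, and agrees with the administered-dose wording of SAP 3.1.1 and 3.2.1. The cumulative reading of the MCRT is firmer, because no 300 mg step exists.

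A reader might infer that the primary threshold is always understated by a third. The documents do not support that: the gap depends on where ED10 lies, and below the first step it can reverse. A reader might also infer that the trial's conclusion would be reversed. The plan sets no test of ED05 or ED10 against 300 mg, Protocol 2.1 states only an expectation and names neither estimate, and desensitization is defined per child. The rates in step 7 of the working rest on a comparison that the plan does not prescribe.

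**Conclusion.** The concern holds as a scale mismatch that the SAP leaves unresolved. The SAP does not state the scale of NOAEL and LOAEL for the ED05/ED10 fit, and its only listed values are single steps. The 300 mg MCRT and the 5000 mg total fit the cumulative scale alone. This is more than a missing detail, because following the listed values gives an estimate that cannot be set beside 300 mg.

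If they are followed, ED10 is about one third too low for a true cumulative ED10 of 400–500 mg, the region where the 300 mg expectation is most sensitive, and about 44% too low at 1000 mg. These sizes assume log-normal thresholds and n = 45. The table of levels and the relabelling of the non-parametric intervals need no distribution. If the sponsor has always meant cumulative dose, the estimate is sound and only the text is at fault.

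**What to change.** In SAP 3.2.1, 3.2.3 and 10.1, including the list of NOAEL values, name one dose scale for NOAEL, LOAEL, ED05/ED10 and the MCRT. If ED05 and ED10 are to be read against 300 mg, the interval limits should be cumulative protein: 0–100, 100–300, 300–800, 800–1600, 1600–2900, 2900–5000 and above 5000 mg. Any step-dose fit should be labelled as such and not compared with 300 mg. Fix this before the 48th month data are analysed.

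The sponsor should also reconcile the wordings of the MCRT criterion. The Synopsis randomizes at 300 mg or more, but its preceding bullet ends the study for a child who cannot exceed 300 mg. The Study Design section, Protocol 5.5 and SAP 4 require more than 300 mg, and SAP 4.3 refers to a 300 mg dose. A child who tolerates the second step and reacts at the third has taken exactly 300 mg, so the wording decides that child's status. Which rule applies is for the sponsor to settle.

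The cost is a few sentences of SAP text and one recoded input column, plus one extra table if the step-dose fit is kept. No visit, challenge or data collection changes.

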1. BACKGROUND

This Statistical Analysis Plan (SAP) has been written to address the concerns identified in the March 19, 2014 protocol abbreviated Peanut SLIT and Tolerance (UNC IRB#11-2308), which included our proposed primary analysis plan aimed at assessing effectiveness of peanut SLIT to induce clinical tolerance 6 months after its discontinuation.

We recognize the investigating team's concerns regarding the assumption that patients will be able to clear the food challenge administered after 6 months of SLIT discontinuation to demonstrate clinical tolerance. The team believes this assumption is rather optimistic, less supported by prior research and suspects that the current study protocol calls for negligible success rate by the end of 6 months of SLIT discontinuation as most of the subjects would fail for clinical tolerance. Since time to loss of desensitization (TLD) is an important dimension that, in our knowledge, no prior study has investigated, provides clinically valuable information and helps facilitate future study design, this study provides an opportunity and a robust framework to study the same. As a result, the revised protocol analyzes a systematic approach to address this concern. We believe that with few changes in the study design and efficacy analysis plan, the revised protocol will help address new objectives of primary enquiry and will provide greater precision to cater to individual's need.

With 51 total enrollees, we are midway through the study's conduct with 24 subjects clearing 48 months of dose maintenance period and waiting to be administered the 48th month food challenge and to be randomized to the placebo or the treatment arm as per the existing protocol. The revised study design calls for amendments beyond the 48 months' period of dose maintenance to include 48th month food challenge followed by discontinuation of SLIT for all subjects for at most 17 weeks, dissolving the need for a two-arm trial. Subjects will be randomized to weekly observed time points during 17 weeks following the 48th month food challenge when the final food challenge will be administered to assess individual's persistent desensitization also known as sustained unresponsiveness (SU). The structure of this final food challenge will be similar to that of the earlier (48th month) food challenge with similar levels of administered drug doses.

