8. GENERAL ISSUES FOR STATISTICAL ANALYSIS

8.1 General Statistical Methodology

Descriptive summaries will be provided where appropriate for each of the primary and secondary variables.

Baseline characteristic and safety tables will be completed for the Safety Population unless otherwise specified. Baseline values are defined as the last non-missing measurement prior to the first dose of study drug. Change from baseline will be defined as the post-baseline visit value minus the baseline value.

Continuous, quantitative, variable summaries will include the number of patients (N) with non-missing values, mean and standard deviation, median, minimum, and maximum. Categorical, qualitative, variable summaries will include the frequency and percentage of patients who are in the particular category. In general the denominator for the percentage calculation will be based upon the total number of patients in the study population unless otherwise specified.

Efficacy tables will be presented for the ITT Population for each of the primary objectives. First, the number and proportion of subjects for each interval of NOAEL and LOAEL observed at the 48th month DBPCFC will be reported. This will be broken by baseline and other clinical characteristics. Non-parametric Kaplan-Meier estimates of NOAEL distribution with interval censoring will be used to report expected proportion of subjects within each interval of NOAEL and LOAEL, overall and by patient groups. Second, for each interval of NOAEL and LOAEL observed at the 48th month DBPCFC, Kaplan-Meier product limit estimates of the probabilities of loss of tolerance (as defined by the latter three efficacy outcomes in section 3.2.1 bullet 2) using interval censoring, will be plotted against time (17 weeks), overall and for various patient groups. The “expected” number of patients with loss of tolerance and the “P values” derived

from univariate log rank tests for interval censored data will be reported for each 48th month DBPCFC NOAEL.

Unless otherwise indicated, all statistical tests will be 2 sided and tested at a significance level of 0.05. Corresponding 95% confidence intervals will be presented for statistical tests.

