8.1.3 Data Handling for Patients who withdraw from the Study

Such subjects will be considered intolerant and failing at time 0.

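### The likelihood printed in SAP 10.1 for time to loss of desensitisation cannot be maximised as written and does not match the per-level analysis it serves

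*SAP*

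**What the plan says.** **Unit of analysis.** SAP 10.1: "for each dose interval bounded by the NOAEL and LOAEL of the 48th month DBPCFC, we will conduct survival analysis with case-1 censoring". SAP 8.1 matches it: p-values "from univariate log rank tests for interval censored data will be reported for each 48th month DBPCFC NOAEL". SAP 1 and 3.1.1 state the aim as time to loss given the dose level reached.

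**Likelihood (SAP 10.1).** X_d and F_d are defined for a given NOAEL d. The observation is (T, Δ), with Δ = I{X_d ≤ T} and t running from 0 to 17. X_d is set to 0 "for those subjects who do not meet MCRT" at the 48-month challenge, and y = I(X = 0). One product over children follows, with a logistic part in γ for X = 0, factors in F_d and 1 − F_d, and hazard `λ0·exp(β'Z)`. Maximising it is said to give β and γ. Z is described only as baseline and clinical covariates.

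**Population.** SAP 7 runs all efficacy analyses on randomised patients. SAP 4.3 makes reaching the MCRT a condition of randomisation. For withdrawals, SAP 8.1.3 says "Such subjects will be considered intolerant and failing at time 0".

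**Later model.** SAP 10.1 adds: "The results from preliminary analyses will help support implementation of advanced and more precise methods".

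**Counts.** SAP 4.3: "three qualified subjects are randomly assigned to one of the final DBPCFC administered each week", for 17 weeks. SAP 1: "With 51 total enrollees, we are midway through" the study, with "24 subjects clearing 48 months of dose maintenance period". The Protocol gives 45 completers (Synopsis), 50 completers (Study Design) and about 45 eligible for randomisation (5.2), each from 55 enrolled.

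**The concern.** This is the only likelihood the SAP prints for the second half of the primary objective, and an analyst could not run it. Each way of making it run is a different model: separate fits per level, one curve for all levels, or level-specific curves with shared covariate effects. They differ in what they estimate and in their power. If the SAP does not choose, the choice will be made with the data in hand.

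Information is scarce. Each randomised child supplies one yes/no answer at one week, so dividing the children by NOAEL before testing covariates costs a great deal.

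**Working it through.** **1. The plan's own figure.** Protocol 8.1.1: 50% v 90%, 2:1, 80% power, two-sided 0.05. Pooled p = (0.9 + 2×0.5)/3 = 0.633. n = [1.96√(0.633×0.367×1.5) + 0.842√(0.09 + 0.25/2)]² / 0.4² = 14.96, so 15 + 30 = 45, and 45/0.9 = 50. The stated 50 reproduces, but for the two-arm comparison that was dropped. It says nothing about time to loss.

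**2. Zero product.** Take a child below the MCRT: y = 1, X = 0, t = 0, so Δ = I{0 ≤ 0} = 1. The contribution is π × F_d(0) = π × (1 − e⁰) = 0. One such child makes the whole likelihood zero. With the F factors raised to the power (1 − y), the child contributes π, as intended.

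**3. γ.**
- *Within a level:* d fixes y, so all children share one value, apart from withdrawals scored at time 0. In a check with 11 children at one passing level, λ held fixed, the log-likelihood was −8.036, −6.714, −6.640 and −6.640 at γ intercepts of −2, −5, −10 and −20. It rises to a plateau, so there is no finite maximum.
- *Across levels, randomised only (SAP 7 with 4.3):* every y is 0, again apart from withdrawals, so the same failure occurs.
- *Across levels, with children who failed the challenge included:* assuming 6 failures and 45 randomised, π = 6/51 = 0.118. This is estimable once step 2 is repaired.

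**4. No dose index.** λ0 carries no d and Z does not name the NOAEL. Assume true level medians of 4, 8, 16 and 32 weeks. The true probability of loss by week 17 is 1 − 2^(−17/median) = 0.95, 0.77, 0.52 and 0.31. The printed hazard fitted across levels returns one median of 10.5 weeks and 0.67 for every level.

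**5. Precision per level.** Cumulative challenge doses are 100, 300, 800, 1600, 2900 and 5000 mg. Five levels qualify if 300 mg cumulative counts as passing. Four qualify if more than 300 mg is needed, or if the single doses listed in SAP 10.1 are compared with 300. The documents word this threshold in more than one way, so both counts are carried. With 45 randomised and an even split: 45/5 = 9 or 45/4 = 11.25 per level.

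Information on log λ per child = mean over weeks 1–17 of x²e^(−x)/(1 − e^(−x)), where x = λt and λ = ln 2/median. At a median of 8.5 weeks this is 0.446.
- n = 9: SE = 1/√(9×0.446) = 0.499; 95% factor exp(1.96×0.499) = 2.66.
- n = 11.25: SE = 0.446; factor 2.40.
- n = 9 with a median of 4 or 17 weeks (information 0.528 or 0.287): 2.46 or 3.38.

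**6. Power for a two-group covariate, hazard ratio 3, median 8.5 weeks (simulation).**

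| Analysis | Power |
|---|---|
| Inside one level, score test | 18–19% (4 v 5 children) to 23% (5 v 6) |
| Inside one level, permutation log-rank | 7% to 10% |
| One score test stratified by level, N = 45 | 63% (five levels), 66% (four) |
| One test, no NOAEL term, N = 45 | 68% |

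Type I error of the stratified test was 5.8% and 5.7%. With the covariate split evenly inside every level, a repeat gave power a few points higher, so about two thirds is a fair reading. Inside one level the hazard ratio had no finite estimate in 31% (4 v 5) and 21% (5 v 6) of trials, because one group was all lost or all kept.

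**7. Counts.** 3 × 17 = 51, the whole enrolment. 55 × 0.9 = 49.5, not 45. 50 × 0.9 = 45 and 51 × 0.9 = 45.9. None of these allows for children who fail the 48-month challenge. The effect is small: with one common rate, the factor is exp(1.96/√(51×0.446)) = 1.51 at 51 and 1.55 at 45.

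**The case against.** The strongest reply is that the intended model can be recovered. SAP 10.1 conditions on d throughout, writes F_d, leaves β and γ without a dose index, and introduces the formula as an illustration. Level-specific curves with shared β then need only a subscript on λ0. This stands, and the fix below adopts it. It does not remove the point: the SAP does not print that model, its text and SAP 8.1 describe analyses inside each level, and the subscript cures neither the zero product nor γ.

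The NOAEL might be counted among the clinical covariates in Z. That is possible but not stated. Its absence from the list in SAP 9.3 proves nothing, because that list is of descriptive baseline summaries.

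Children who fail the challenge may be meant to be in the analysis. SAP 8.1.2 gives them a time of zero, and SAP 4 places randomisation at the 48-month visit. On that reading γ is estimable across levels. But SAP 4.3 with SAP 7 excludes them, so the population has to be stated.

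Conditioning on dose level is a stated aim. A smooth log-dose slope would change what is estimated, so preferring it would be taste. This stands too.

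The endpoints are worded as estimates, and no within-level test is called confirmatory. That limits the weight of the power figures, but p-values are still planned per level.

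**Conclusion.** The point holds. As printed, the likelihood is zero once a child below the MCRT enters, cannot estimate γ in the stated population, and loses the dose level when fitted across levels. These three findings follow from the text, with the withdrawal exception noted. The cost of separate testing, about 18–23% against 63–66% power, rests on assumptions that the documents do not supply: 45 randomised, an even split, uniform weeks, exponential loss, median 8.5 weeks and hazard ratio 3. It should be corrected before analysis.

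A reader might infer more, and the documents do not support it:
- *That time to loss cannot be studied with this design.* A level-stratified model recovers most of the power.
- *That false positives are inflated.* Simulated type I error of the score tests was 4.2–6.5%.
- *That the double-censoring model replaces the primary analysis.* SAP 10.1 still calls its two parts primary; the relation only needs stating.
- *That the conflicting counts undermine the trial.* A pre-generated list with unfilled slots is ordinary, and 1.51 v 1.55 is immaterial.

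**What to change.** **In SAP 10.1:**
- Print the likelihood as the product over children of `π^y · {(1 − π)·[1 − F_d(t)]^(1−δ)·F_d(t)^δ}^(1−y)`, so that the F terms apply only when y = 0.
- Make the primary model `λ = λ0d·exp(β'Z)`, with a separate baseline rate for each 48-month NOAEL level and β shared. Test each covariate with one level-stratified test.
- Fit the logistic part on all children who take the 48-month challenge, name that population beside SAP 7, and say how withdrawals scored at time 0 enter.
- State that the double-censoring model does not replace this analysis.
- Optionally, pre-specify a log-NOAEL slope in place of λ0d as a sensitivity analysis for narrower per-level rates.

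**In SAP 8.1:** label the per-level log-rank p-values descriptive.

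**Clean-up:** reconcile the 45 and 50 completers, the roughly 45 eligible for randomisation and the 51 slots. Say in SAP 4.3 that three per week is a maximum. Run the simulation promised in SAP 6 at the expected number randomised, allowing for children who fail the 48-month challenge, rather than at the 51 enrolled.

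**Cost:** wording, one subscript, one exponent and a simulation already promised. The model assumes one covariate effect at all levels. Per-level rates stay wide (×/÷2.4–2.7 under the same assumptions), and a level where every child is lost or every child is kept still has no finite rate.
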